4.2 Primary Endpoints

We will examine if a single-session tDCS will reduce depression-related negative attention bias before and after the stimulation using the attention bias scores generated using reaction-time based data during the dot probe and visual search task. We will also compare this difference across conditions.

4.3 Secondary Endpoints

Measure if tDCS administration can improve negative/depressive mood and affect measured using self-reported questionnaires before and after tDCS, as well as across conditions.

5 Study Enrollment and Withdrawal

5.1 Inclusion Criteria

In order to be eligible to participate in this study, an individual must meet all of the following criteria:

1. Aged 18-45
2. Female
3. Depression group only: Mild to moderate depression (determined by BDI-II scores of 14-19 and 20-28, respectively).
4. If taking antidepressants, medication must be stable ≥ 30 days prior to screening
5. Health control group only: Minimal depression (determined by BDI-II scores of 0-13).

5.2 Exclusion Criteria

An individual who meets any of the following criteria will be excluded from participation in this study:

1. Wide-Range Achievement Test-Fourth Edition (WRAT-4) Reading Subtest standard score <85 (to ensure understanding of test procedures)
2. Insufficient visual and motor ability to operate the intervention and assessments as judged by treating neurologist or study staff
3. Primary neurologic condition that would prevent ability to participate
4. History of head trauma in the last year
5. Medical device implants in the head or neck
6. History or current uncontrolled seizure disorder

CONFIDENTIAL

7. Current substance abuse disorder
8. Pregnant or lactating women
9. Skin disorder/sensitive skin near stimulation locations
10. Depressed participants only:
11. Primary psychiatric disorder other than depression (based on MINI, only for the mild to moderate depression group)

Source documents for inclusion/exclusion criteria can include subject self-report, medical records, case report forms, and eligibility checklists. Criteria asked during the phone pre-screen will be reconfirmed after consent is obtained.

5.3 Vulnerable Subjects

Vulnerable subjects will not be recruited for this study.

5.4 Strategies for Recruitment and Retention

Subjects will be recruited through NYU Langone's iConnect, clinicaltrials.gov, word of mouth, and research flyers placed in the NYU Langone and NYC community. We will also use email blasts (e.g., listserv) to NYC schools and community (an email script attached separately). Interested participants will be able to contact a study team member via phone or e-mail. A team member will respond by phone to provide potential participants an overview of the study, including study procedures, and risks and benefits, using an IRB-approved phone script. Potential participants will be clearly informed that they have the right not to participate in the study. If interested, subjects can complete a general eligibility pre-screen over the phone. Subjects will additionally verbally confirm if they meet eligibility criteria.

5.5 Total Number of Participants and Sites

Recruitment will end when approximately 25 participants are enrolled for each condition (Total N = 75). It is expected that approximately 25 participants will be enrolled in order to produce 20 evaluable participants per each group (Total N = 60) for this pilot study.

5.5.1 Use of Epic Information for Recruitment Purposes

N/A

5.6 Duration of Study Participation

Subject participation will consist of a single visit lasting approximately 2.5 hours and will include:

- Obtain written consent (~25 minutes)
- Eligibility screening (15 minutes)
- Mood Questionnaires (30 minutes)
- Attention Bias Tasks (DP & VS, 60 minutes)
- tDCS session (30 minutes)

6 Study Schedule

6.1 Pre-Screening

- Team member conducts phone pre-screening (including BDI-II) to determine general eligibility based on inclusion/exclusion criteria. Participants who meet the BDI-II criteria during the phone screen will not be required to repeat it if they schedule their visit within 2 days of the phone screen. Completing the BDI-II over the phone is a practical option that helps screen out those who are ineligible before

CONFIDENTIAL

they travel to clinic and it is suitable for phone use as participants can verbally rate the BDI-II statements on a scale from 0-4.

Those who score in the severely depressed range (29-63) will be offered to contact the NYU Langone Psychiatry Associates at [contact], or if outside the NY area the Substance Abuse and Mental Health Services Administration (SAMHSA) hotline at [name].

All data collected for the purposes of the eligibility pre-screening will be destroyed immediately if the potential subject is ineligible or does not sign an informed consent form at their baseline.

6.2 Screening/Study Visit

- Obtain written informed consent (*25 minutes or however much time is needed*).
- Conduct eligibility screening/MINI/BDI-II (*15 minutes*)
- tDCS tolerability test (*2 minutes*)
- Administer depression surveys (BAI, HAM-D, and SMDDS) (*15 minutes*)
- Administer computerized attention bias dot-probe and visual search task (*30 minutes*)
- Administer pre-tDCS measures (PANAS and AMS; *10 minutes*)
- Complete tDCS session (*30 minutes*)
- Repeat PANAS and AMS (*10 minutes*)
- Repeat attention bias dot-probe task and visual search (*30 minutes*)

7 Study Procedures/Evaluations

After participants provide written informed consent, the following study procedures will take place during a single 2.5 hour research visit:

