Statistical Analysis	Pre-post tDCS comparison analyses using t-tests and correlations

CONFIDENTIAL

Schematic of Study Design

Pre-Screen	
• Eligibility pre-screen to determine general eligibility including BDI-II screen
Study Visit	
• Obtain Informed Consent• Mini International Neuropsychiatric Interview (MINI) (Screening)• Beck Depression Inventory (BDI-II) (Screening)• Beck Anxiety Inventory (BAI)• Hamilton Depression Rating Scale (HAM-D)• Symptoms of Major Depressive Disorder Scale (SMDDDS)• Healthy controls will complete a brief computer-based word puzzle task before the tDCS session, assigned to one of two conditions: difficult/unsolvable or easier
Pre-tDCS Administration	
• Positive and Negative Affect Schedule-SF (PANAS);• Analog Mood Scale (AMS)• Dot Probe Task (DP) and Visual Search (VS) Task
tDCS Administration	
• tDCS tolerability test• 30 minutes of tDCS (up to 2.0mA)
Post-tDCS Administration	
• PANAS• AMS• DP and VS Tasks

CONFIDENTIAL

Key Roles

Principal Investigator:

[name]
NYU Langone Health
Department of Neurology
[name]
[contact]
[contact]

Sub-Investigators:

[name]
NYU Langone Health
Department of Neurology
[name]
[contact]
[contact]

[name]
Department of Neurology, NYU Langone Health
[name]
[name]
[contact]
[contact]

1 Introduction, Background Information and Scientific Rationale

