7.4.2 Visual Search Task

In addition, the Visual Search task (e.g., Wolf & Horowitz, 2017) will be administered to further assess attention bias, particularly examining the interference and facilitation effects in attention using emotional stimuli (Rinck & Becker, 2005). The task uses emotional faces or words as stimuli, where the participant is instructed to search for the face that does not fit into the search set with respect to gender (i.e., the only male under three female faces, or the only female under three male faces), where the target and distractors are expressing different or same emotions (i.e., neutral-neutral, sad-neutral, happy-neutral, neutral-sad, neutral-happy, sad-sad, and happy-happy). Studies have shown that individuals with emotional and stress-related disorders show interference effect (i.e., emotional stimuli being the distractor) and facilitation effect (i.e., emotional stimulus being the search target), but less is known about depression (Bodenschatz et al., 2021; Rinck & Becker, 2005; Pineles et al., 2009). This study will use this task as an outcome measure of AB alongside the DP task. For this task, mean response time (the time between display onset and button press) to the target stimulus for each stimulus type is measured as the main outcome variable.

7.5 tDCS Session

tDCS Dose Selection and Tolerability: Participants will undergo a tolerability test to ensure tolerance of the stimulation intensity. In under 2 minutes, the tDCS device ramps up to the target stimulation of 2.0mA and ramps back down to 0mA. The tolerability test can be aborted at any time if the participant is uncomfortable. If 2.0mA stimulation is not tolerated, the participant will be given the option to proceed with a second tolerability test at a lower stimulation amperage (1.5 mA). Participants who cannot tolerate 1.5mA will be excluded as a screen failure.

tDCS settings: The MINDD STIM tDCS system is composed of a management component, treatment module, single-use sponge patches and supporting patches, a headband to hold in position the sponge patches, and 2 cables. A trained study technician will program the stimulation device through the management component setting to the following stimulation parameters:

- **Stimulation intensity:** 2.0 mA or 1.5 mA
- **Stimulation duration:** 30 minutes
- **Ramp up duration:** 30 seconds (beginning of stimulation)
- **Ramp down duration:** 30 seconds (end of stimulation)

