11.3 Statistical Methods

For the study hypothesis to examine the preliminary effect of a single-session tDCS on depression on negative attention bias, we will use the calculated latency response times pre-tDCS and post-tDCS using the DP and VS tasks and compare change using a paired sample's t-test for each measure. Further, to compare across the groups, we will use ANOVA for before and after effect of tDCS on negative attention bias across the three groups.

As secondary and exploratory, we will also test change in pre- to post- ratings of depressive symptoms and affect. These findings will be collected to inform the power analyses for a larger controlled trial.

12 Source Documents and Access to Source Data/Documents

Source data is all information, original records of clinical findings, observations, or other activities in a study necessary for the reconstruction and evaluation of the study. Source data are contained in source documents. Examples of these original documents, and data records include: hospital records, clinical and office charts, laboratory notes, memoranda, evaluation checklists, pharmacy dispensing records, recorded data from

CONFIDENTIAL

automated instruments, copies or transcriptions certified after verification as being accurate and complete, subject files.

The study case report form (CRF) is the primary data collection instrument for the study. All data requested on the CRF must be recorded. All missing data must be explained. If a space on the CRF is left blank because the procedure was not done or the question was not asked, write "N/D". If the item is not applicable to the individual case, write "N/A". All entries should be printed legibly in blue or black ink. If any entry error has been made, to correct such an error, draw a single straight line through the incorrect entry and enter the correct data above it. All such changes must be initialed and dated. DO NOT ERASE OR WHITE OUT ERRORS. For clarification of illegible or uncertain entries, print the clarification above the item, then initial and date it.

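### Section 6.2 places the active-current tolerability test before the pre-tDCS outcome baselines and the schematic places it after them; one order is needed, with those baselines taken before any current

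*Combined protocol and SAP*

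**What the plan says.** Section 6.2 sets out the visit as a list. After consent and the eligibility screen (MINI and BDI-II) comes "tDCS tolerability test (*2 minutes", then "Administer depression surveys (BAI, HAM-D, and SMDDS) (*15 minutes", then "Administer computerized attention bias dot-probe and visual search task (*30 minutes", then "Administer pre-tDCS measures (PANAS and AMS; *10 minutes", then the 30-minute session, then the repeats.

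The Schematic of Study Design has a Pre-tDCS Administration row holding PANAS, AMS and "Dot Probe Task (DP) and Visual Search (VS) Task". The next row, tDCS Administration, opens with "tDCS tolerability test".

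Section 7.5 (tDCS Session) describes the test: "In under 2 minutes, the tDCS device ramps up to the target stimulation of 2.0mA and ramps back down to 0mA". Someone who does not tolerate this may try a second test at 1.5 mA, and someone who cannot tolerate 1.5 mA counts as a screen failure.

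For the primary analysis, section 11.3 says "we will use the calculated latency response times pre-tDCS and post-tDCS". It compares them by paired t-test for each task and then uses ANOVA across the three groups.

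**The concern.** The two schedules disagree on whether participants have already received active current when the outcome baselines are taken. In most trials a short device check would be a minor matter of visit logistics. Here the baseline carries more weight for three reasons. All three groups receive active tDCS and there is no sham arm, so each participant's own baseline is the only reference for change. Section 4.1 says the study is looking for subtle latency changes at the millisecond level. Section 11.1 wants the control data to supply expected ranges of change for the tasks. If first exposure to current moves attention, arousal or self-rated mood, a baseline taken under 6.2 has already absorbed part of that. If some participants follow 6.2 and others the schematic, their change scores do not mean the same thing.

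**Working it through.** **1. The two orders side by side**

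| Step | Section 6.2 | Schematic |
|---|---|---|
| 1 | Consent | Consent |
| 2 | Eligibility, MINI, BDI-II | MINI, BDI-II |
| 3 | **Tolerability test** | BAI, HAM-D, SMDDS; word puzzle (controls) |
| 4 | BAI, HAM-D, SMDDS | PANAS, AMS |
| 5 | Dot-probe, visual search | Dot-probe, visual search |
| 6 | PANAS, AMS | **Tolerability test** |
| 7 | 30-minute session | 30-minute session |
| 8 | PANAS, AMS | PANAS, AMS |
| 9 | Dot-probe, visual search | Dot-probe, visual search |

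The list in 6.2 runs from consent to repeat measures, so it reads as chronological. Section 7.5 does not settle the matter. It describes the test together with the session, after the task sections, which fits the schematic. It also makes failure a screen failure, which fits the early position in 6.2. No other section reconciles them.

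**2. Gap between test and baseline under 6.2** (listed durations; breaks and the word puzzle, which 6.2 does not place, are ignored)
- Test to start of bias tasks: 15 min of surveys.
- Test to PANAS/AMS: 15 + 30 = 45 min.

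**3. Size of the exposure.** The documents give no charge figure, so this is only a scale check. Inputs from 7.5: 2.0 or 1.5 mA, 30-minute session, 30-second session ramps, test in under 2 minutes. Assumptions: the test lasts the full 120 s; session ramps fall inside the 30 minutes; the test profile is either a plain ramp up and down (triangle) or 30 s ramps with a 60 s hold.
- Session at 2.0 mA: 2.0 × 1740 + 2 × (0.5 × 2.0 × 30) = 3540 mC. At 1.5 mA: 1.5 × 1740 + 2 × (0.5 × 1.5 × 30) = 2655 mC.
- One test at 2.0 mA, triangle: 0.5 × 2.0 × 120 = 120 mC; 120/3540 = 3.4%.
- One test at 2.0 mA, with hold: 2.0 × 60 + 2 × (0.5 × 2.0 × 30) = 180 mC; 180/3540 = 5.1%.
- Two tests (2.0 then 1.5 mA), triangle: 120 + 90 = 210 mC; 210/2655 = 7.9%.
- Two tests, with hold: 180 + 135 = 315 mC; 315/2655 = 11.9%.
- Ceiling for one test, full current for all 120 s with no ramp: 240/3540 = 6.8%. The described ramping rules this out.

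Using the full 120 s overstates the duration, the hold is not described in the text, and a test that was not tolerated may have been aborted early. The two-test figures in particular lean high.

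**4. How a shift would enter the analysis.** Let δ be the mean shift that the test causes in a baseline measure. The test precedes the post-session measures in both orders, so only the baseline differs.
- All participants in the 6.2 order: estimated mean change = true change − δ.
- A fraction p in the 6.2 order: estimated mean change = true change − pδ, and the mixing adds p(1 − p)δ² to the variance of change.
- Group comparison with a common order: biased only by the difference in δ between groups; a shared δ cancels.

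If δ has the same sign as the session effect, the change is diluted. If it has the opposite sign, the change is inflated. The documents give no value for δ.

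**The case against.** The best defence is that 6.2 is deliberate. Tolerability failure is a screen failure, so testing early avoids putting an ineligible participant through outcome testing. The exposure lasts under 2 minutes, the tasks follow about 15 minutes later and the mood ratings about 45 minutes later, and section 2.1 lists only mild sensations. If everyone follows one order at this single site, a shift shared by all groups drops out of the group comparison. The study is also an exploratory pilot.

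Most of this stands as a limit on size. It does not remove the contradiction, and it does not help the within-group paired tests, where a shared shift does not cancel.

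Two stronger readings are tempting and the documents do not support them. A reader might infer that under 6.2 nothing at all is measured before stimulation. In fact MINI and BDI-II come before the test; they are not repeated after the session, so the gap concerns the repeated outcomes only. A reader might also infer that an uncomfortable test lowers baseline mood and that recovery then passes for improvement. Under 6.2 that would require the effect to last about 45 minutes to PANAS/AMS, and nothing in the documents shows this.

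**Conclusion.** The inconsistency is established from the text. If 6.2 is followed, the dot-probe, visual search, PANAS and AMS values used as pre-tDCS are all taken after brief active current. The charge is small: about 3% to 5% of the session for one test, and about 8% to 12% for two, on assumptions that lean high. Charge does not measure sensation or expectancy, so these percentages do not bound the shift. Its size and direction are unknown, and it could be nil.

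The documents do not show that the baseline is biased, nor which order is used in practice. What they support is narrower: the status of the baseline is ambiguous in a study with no sham arm whose primary result is pre-post change. Section 7.5 provides for side effects of the session to be recorded but specifies no such rating for the test, so the question could not easily be examined afterwards. The point is worth correcting because the correction is cheap. No sample size or power figure changes.

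**What to change.** Reconcile section 6.2, the schematic and section 7.5 into one order for all participants, with the baseline dot-probe, visual search, PANAS and AMS completed before any current is delivered. The schematic already shows this. The same edit can settle whether PANAS/AMS come before or after the tasks and where the word puzzle falls, since 6.2 and the schematic differ on the first and 6.2 omits the second. The tolerability criteria and intensities are not at issue and should be left as they are.

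Record for each participant the order used and whether one or two tests were given. Flag anyone already assessed in the 6.2 order so that the primary comparisons can be repeated without them.

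Cost: no added procedure. A participant who then fails the test has already spent 30 + 10 = 40 minutes on outcome baselines, or 55 with the 15 minutes of surveys. A healthy control may also have done the word puzzle, possibly the difficult version, and used a place in the alternating assignment of section 4.1. The plan should say that such a place is refilled, so that the easy and difficult groups stay balanced.

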7.1 Screening

The PI (or team members with PhD or MA in a related field who are trained by the PI) will meet with the participant to review eligibility according to the inclusion/criteria including and administer the mood disorders portion of the Mini International Neuropsychiatric Interview (MINI). Data from screen failures will be deleted immediately after the recruitment period ends.

7.2 Mood and Depression Questionnaires

Participants will be asked to complete self-report questionnaires to assess their baseline depressive symptoms and mood.

7.3 Word Puzzle (Anagram) Task

Half of the healthy control participants ($n = 25$) will receive a difficult anagram task, consisted of medium to difficult mixed letter words (i.e., anagrams; e.g, TAEIGNS = TEASING). The other half ($n = 25$) will receive an easy anagram task for comparison). The task has been well-validated and used successfully in previous research to induce mild stress in healthy controls and those who are at risk for affective disorders (Bishop, 2009; Mogg et al., 1990; Wen & Yoon, 2019). Some of the words in the difficult anagram task are not solvable as real words. Participants will be instructed to solve 40 anagrams as accurately and quickly as possible and they will have 3 minutes to complete the task. The participants will be given a paper and pencil to write down their solutions, and all words will be programmed into present one word at a time on a laptop screen.

7.4 Attention Bias Tasks

Participants will be asked to complete two attention bias assessments: Dot-Probe Task and Visual Search Task.

7.4.1 Dot Probe Task

The dot probe task is an established procedure for measuring and manipulating biases in attention associated with depression in adults and children (MacLeod, Mathews, & Tata, 1986; Eldar et al., 2008, Joormann &

CONFIDENTIAL

Gotlieb, 2007; Pekham et al., 2010). The dot-probe task will be used to assess depression-related attention bias before and after tDCS administration.

To complete the Dot-Probe task, participants will be shown two emotional images (e.g., sad and neutral pair or happy and neutral pair) simultaneously followed by a target in the location of one of the emotional images. Response latencies to targets replacing either the negative/positive or neutral images will be measured before and after training which will be the primary study outcome. Emotional stimuli used are a selection of negative, positive, and neutral pictures taken from a standardized and often used set of emotional faces called the racially diverse affective expression [RADIATE; Conley et al., 2018].

7.4.2 Visual Search Task

In addition, the Visual Search task (e.g., Wolf & Horowitz, 2017) will be administered to further assess attention bias, particularly examining the interference and facilitation effects in attention using emotional stimuli (Rinck & Becker, 2005). The task uses emotional faces or words as stimuli, where the participant is instructed to search for the face that does not fit into the search set with respect to gender (i.e., the only male under three female faces, or the only female under three male faces), where the target and distractors are expressing different or same emotions (i.e., neutral-neutral, sad-neutral, happy-neutral, neutral-sad, neutral-happy, sad-sad, and happy-happy). Studies have shown that individuals with emotional and stress-related disorders show interference effect (i.e., emotional stimuli being the distractor) and facilitation effect (i.e., emotional stimulus being the search target), but less is known about depression (Bodenschatz et al., 2021; Rinck & Becker, 2005; Pineles et al., 2009). This study will use this task as an outcome measure of AB alongside the DP task. For this task, mean response time (the time between display onset and button press) to the target stimulus for each stimulus type is measured as the main outcome variable.

7.5 tDCS Session

tDCS Dose Selection and Tolerability: Participants will undergo a tolerability test to ensure tolerance of the stimulation intensity. In under 2 minutes, the tDCS device ramps up to the target stimulation of 2.0mA and ramps back down to 0mA. The tolerability test can be aborted at any time if the participant is uncomfortable. If 2.0mA stimulation is not tolerated, the participant will be given the option to proceed with a second tolerability test at a lower stimulation amperage (1.5 mA). Participants who cannot tolerate 1.5mA will be excluded as a screen failure.

tDCS settings: The MINDD STIM tDCS system is composed of a management component, treatment module, single-use sponge patches and supporting patches, a headband to hold in position the sponge patches, and 2 cables. A trained study technician will program the stimulation device through the management component setting to the following stimulation parameters:

- **Stimulation intensity:** 2.0 mA or 1.5 mA
- **Stimulation duration:** 30 minutes
- **Ramp up duration:** 30 seconds (beginning of stimulation)
- **Ramp down duration:** 30 seconds (end of stimulation)

Participant preparation for tDCS session: The trained study technician will prepare the stimulation electrodes as detailed below:

- Two single-use sponge patches will be (1) inserted in the patch supporters and (2) soaked with saline solution.
- The patches will be then attached to the headband in the positions corresponding to the frontal region. The red patch (anode) will be located on the left frontal region while the blue patch (cathode) on the right region frontal region.
- The headband will be then positioned on the participant's head.
- The stimulation module will be then attached to the electrode cables.

CONFIDENTIAL

- The study technician will connect the stimulation module via Bluetooth to the management station and then will be ready to initiate the stimulation session.

tDCS session: Participants will complete a single 30 minutes tDCS session targeting the left DLPFC while sitting in a comfortable position. At the end of the tDCS session possible side effects experienced during the tDCS session will be recorded along with their intensity (rated using the visual analogue scale, 0-10) and duration. The session can be aborted at any time for any reason if the participant wishes.

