9.2 Recording of Adverse Events

At each contact with the subject, the investigator must seek information on adverse events by specific questioning and, as appropriate, by examination. Information on all adverse events should be recorded immediately in the source document, and also in the appropriate adverse event module of the case report form (CRF). All clearly related signs, symptoms, and abnormal diagnostic procedures results should be recorded in the source document, though should be grouped under one diagnosis.

CONFIDENTIAL

All adverse events occurring during the study period must be recorded. The clinical course of each event should be followed until resolution, stabilization, or until it has been determined that the study treatment or participation is not the cause. Serious adverse events that are still ongoing at the end of the study period must be followed up to determine the final outcome. Any serious adverse event that occurs after the study period and is considered to be possibly related to study participation should be recorded and reported immediately.

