11.2 Sample Size Determination

The primary objective of this study is to test change in negative attention bias in people with mild to moderate depression following a single session of DLPFC tDCS, and see if their outcomes differ from that of healthy controls.

This is a pilot study to assess the feasibility of a single-session tDCS in a small sample, and the findings will provide preliminary evaluation of effect and inform power analyses for use in a clinical trial design.

A total of $N = 75$ ($n=25$ participants for each group) will be enrolled to obtain evaluable target of $N=60$ ($n = 20$ for each group) based on the estimated number of eligible participant for each group contacts across the study period.

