14.2 Study Records Retention

Study documents will be retained for the longer of 3 years after close out or 5 years after final reporting/publication. These documents should be retained for a longer period, however, if required by local regulations.

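### People who receive current and cannot tolerate 1.5 mA become screen failures whose data are deleted, so test-stage intolerance is missing by construction from the retained participant-level data

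*Combined protocol and SAP*

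**What the plan says.** The tolerability test in section 7.5 (tDCS Session) delivers real current: "In under 2 minutes, the tDCS device ramps up to the target stimulation of 2.0mA and ramps back down to 0mA". A first failure does not end participation: "If 2.0mA stimulation is not tolerated, the participant will be given the option to proceed with a second tolerability test", this time at 1.5 mA. The session settings accordingly allow "2.0 mA or 1.5 mA". For those who fail the lower test: "Participants who cannot tolerate 1.5mA will be excluded as a screen failure".

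Section 7.1 (Screening) fixes what happens to such records: "Data from screen failures will be deleted immediately after the recruitment period ends". It lists no exemption.

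Four other places bear on the same people:

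- Section 9.2: "All adverse events occurring during the study period must be recorded". It also requires each event to be followed to an outcome, and it makes no exception for screen failures.
- Section 11.2: "This is a pilot study to assess the feasibility of a single-session tDCS in a small sample".
- Section 14.2: "Study documents will be retained for the longer of 3 years after close out or 5 years after final reporting/publication".
- Sections 10.5.2 and 13.4.1: usable data from participants who withdraw or are terminated may be kept, and data already collected from someone who asks to leave stay in storage.

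**The concern.** Each rule is unremarkable alone. Applied in sequence, they erase the records of consented people who were exposed to the device and stopped because of it. These are the people who carry the information on test-stage intolerance, and they drop out of both numerator and denominator.

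Two things are at stake. The first is the safety record. An adverse event during the test must be recorded and followed under 9.2, yet the participant's data are due for deletion under 7.1, and nothing says which rule prevails. The second is feasibility. The pilot is meant to inform a later trial, and the share of consented people who cannot start stimulation is a basic planning input. A figure taken from the retained data would be biased towards good tolerance at that stage.

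The treatment of similar people is also uneven. Someone who stops one minute into the 30-minute session can keep a usable record, while someone who stops during the test loses theirs.

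**Working it through.** **1. The plan's own figures.** Sections 5.5 and 11.2 give 75 enrolled (25 per group) to obtain 60 evaluable (20 per group). The implied loss is 1 − 60/75 = 20%, and 60/0.80 = 75, so the figures agree. The 20% is not stated, and neither section gives an intolerance rate. There is therefore no stated tolerability figure to reproduce.

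**2. Following the rules for one participant.**

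- Consent comes first (6.2), so the person is in the study when tested.
- Current is delivered in the test (7.5), so the person is exposed.
- Failing at 1.5 mA makes the person a screen failure (7.5), although intolerance is not among the exclusion criteria in 5.2.
- Screen-failure data are deleted once recruitment ends (7.1).
- Side-effect ratings are specified only for the end of the session (7.5), so no rating is specified for the test itself.

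The number of 1.5 mA test failures in the retained participant-level data is therefore zero whatever the true rate.

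**3. How much is deleted per person.** Section 6.2 puts the test before the surveys and attention tasks. The Schematic of Study Design puts it under tDCS administration, after the control group's word puzzle and all baseline measures. Under the second order, deletion would also remove completed baseline data and controls already assigned to a puzzle condition.

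**4. Size.** Let p be the true rate of failing the test. This is an assumption, since the documents give no value; the range used is 1% to 10%. Assume also that 75 people must pass.

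- Expected failures deleted = 75p/(1 − p)
- Chance of at least one failure among the first 75 tested = 1 − (1 − p)^75

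| Assumed p | Expected failures deleted | Chance of at least one |
|---|---|---|
| 1% | 0.8 | 53% |
| 2% | 1.5 | 78% |
| 5% | 3.9 | 98% |
| 10% | 8.3 | >99.9% |

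In each row the retained data show 0/75. The exact (Clopper-Pearson) 95% upper limit is 1 − 0.025^(1/75) = 4.8%.

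**5. What keeping the failures would show.** For whole numbers of failures x, with 75 + x tested:

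| x | Proportion | Exact 95% CI |
|---|---|---|
| 1 | 1/76 = 1.3% | 0.03% to 7.1% |
| 2 | 2/77 = 2.6% | 0.3% to 9.1% |
| 4 | 4/79 = 5.1% | 1.4% to 12.5% |
| 8 | 8/83 = 9.6% | 4.3% to 18.1% |

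These counts are illustrations, not estimates. If test failures instead count within the 75 enrolled, the proportions change little: 4/75 = 5.3% (1.5% to 13.1%) and 8/75 = 10.7% (4.7% to 19.9%).

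**The case against.** A reader might infer that the pilot's whole tolerability record is forced to 0% intolerance. The documents do not support that. Side effects in the 30-minute session are recorded with intensity and duration, and the session can be aborted (7.5). Step-downs remain visible as sessions delivered at 1.5 mA. The investigator reviews side effects and screen failures at intervals of four months or less (10.1). Only failure of the 1.5 mA test is forced to zero.

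A reader might also infer that all safety data on these people would be lost. That too goes beyond the text. Section 9.2 still requires events to be recorded when they occur, and copies of reports to the IRB are kept in the study file (9.3.1). The deletion sentence stands in the eligibility section and could be meant for eligibility data only. Section 6.2 lists the test straight after eligibility screening, which gives the screen-failure label some support.

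Finally, tolerability is not a primary or secondary endpoint (4.2, 4.3), and 11.2 names feasibility without a measure. At a 1% failure rate the distortion is small: 1/76 has an interval of 0.03% to 7.1%, against 0 to 4.8% for 0/75.

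These points limit the scope. They do not remove the contradiction. Section 7.1 does not say that adverse event records, counts or reasons survive, and periodic review of screen failures does not guarantee that anything is kept or reported. A narrower meaning for the deletion sentence is possible, but the text does not state it.

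**Conclusion.** The point holds for the test stage. Followed as written, 7.5 and 7.1 remove intolerance of 1.5 mA from the retained participant-level data. That conflicts with recording and following all adverse events (9.2) and with the general retention rule (14.2), and it undercuts the feasibility aim (11.2). The broader readings, that all intolerance or all safety information disappears, are not supported.

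The size depends on an unstated rate. With 75 people required to pass and an assumed failure rate of 1% to 10%, between 0.8 and 8.3 failures are expected to be deleted, and 0/75 is retained throughout. The effect is negligible at the low end. At the high end it matters for planning, because 8/83 = 9.6% lies well above the 4.8% upper limit that the retained data would suggest. No primary or secondary endpoint in 4.2 or 4.3 measures test-stage tolerance; the cost falls on the safety and feasibility record. Deletion cannot be undone, so the wording should be settled before recruitment ends.

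**What to change.** In 7.1, exempt from deletion the de-identified, ID-coded record of everyone who received current in the tolerability test: group, intensities attempted, reason for stopping, and adverse events. Keep it under 14.2, with a cross-reference in 7.5. Include anyone who fails at 2.0 mA and declines the second test, since 7.5 does not define that person's status. Reconcile the position of the test in 6.2 with the schematic, so that it is clear which baseline data exist for these people.

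In 11.3, add one descriptive feasibility result: the number not tolerating the test, with all those tested as denominator and an exact 95% CI. No hypothesis test is needed.

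The tolerability rule, the stimulation settings and who goes on to the session stay unchanged; this is a matter of retention and reporting only. The cost is a wording change, possibly one sentence in the consent form, and a slightly less favourable tolerability figure.
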